The purpose of the study is to test the question of: Does the addition of 0.5ml 1% lidocaine compared to 0.5 ml normal saline solution to 1.2 million units of benzathine penicillin G affect the pain experienced by individuals being treated for Treponema pallidum (syphilis) infections at 10 minutes and 24 hours post injection?

B Background

B1 Prior Literature and Studies, and Rationale for this Study

There is evidence to suggest that lidocaine can help reduce the pain associated with intramuscular injections of benzathine penicillin G or bicillin, used to treat syphilis

infections. A study published in the Journal of Pediatric Infectious Diseases in 1998 found that the use of lidocaine as a diluent of BPG significantly reduced the pain of injection. Another study by Estrada et al in 2019 looked at the addition of 1% mepivicaine as diluent for PGB vs PGB alone and showed that mepivicaine significantly decreased pain experienced by participants. Per the IUSTI European Guidelines for Syphilis management, lidocaine is used as a diluent for benzathine penicillin G since 1998. No studies have been performed thus far looking at prefilled benzathine penicillin G syringes and the possibility of inserting lidocaine to the injection to decrease the pain experienced by individuals being treated for syphilis infections, instead of using lidocaine as a diluent which is not possible for the BPG formulations present here in the US. in the US.

C Study Objectives

C1 Primary Aim

To see if there is any benefit of adding 0.5 ml 1% lidocaine to prepackaged Benzathine Penicillin G, with respect to pain, compared to standard of care, in the treatment of Treponema pallidum infections, both 10 minutes and 24 hours after injection.

C2 Secondary Aim

To see if there are any adverse effects of adding 0.5 ml 1% lidocaine to prepackaged Benzathine Penicillin G and to assess use of other pain medications 24 hours post injection.

D Investigational Agent

D1 Preclinical Data

1% lidocaine has been added as a solvent for BPG in other countries around the world.

D2 Clinical Data to Date

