- 3- The participant will then be taken to a clinic room, and be shown the consent form. Study design will be explained to them including them receiving the same treatment they would normally but with one injection with 0.5 ml normal saline and one with 0.5 ml 1% lidocaine. They will then be asked if they have any questions and if they choose to consent, they will sign a physical consent form that will then be uploaded into their chart. (30-45 minutes)

2.d Randomization Method and Blinding

Both clinicians and participants will be blinded to the contents of the syringes. Only the nursing staff will know which syringe contains lidocaine and which contains normal saline as they will be drawing up the contents into the syringes, after which they will designate L and R on the syringes and in a log book which will designate which syringe had lidocaine and which had normal saline. This log book will be kept separate from clinicians and participants until study completion. Each participant will have a unique code that will be included in the log book, where the nurse who fills the syringes will state which side, left or right, contained lidocaine and which contained normal saline. This log book will then be used to cross reference injection sites and the survey results during the analysis phase, in a way that allows the data to be de-identified.

2.e Risks and Benefits

Risks

Risks are rare and mainly involve injection site pain, allergic reaction. Some risks, if severe, may cause death.

Likely / Common

Mild

- Pain at injection site (BPG)
- Headache (lidocaine)

- Transient pain (lidocaine)
- Edema (lidocaine)

Less Likely / Less Common

Mild

- Hypersensitivity Rash (BPG)
- Diarrhea (BPG)
- Agitation (lidocaine)
- Anxiety (lidocaine)
- Confusion (lidocaine)
- Dizziness (lidocaine)
- Lethargy (lidocaine)
- Tinnitus (lidocaine)

Rare

Life Threatening

• Hypersensitivity- anaphylaxis (BPG and Lidocaine)

Serious

- Neutropenia (BPG high doses)
- Hyperreflexia (BPG high doses)
- Myoclonus (BPG high doses)
- Seizure (BPG high doses)
- Acute interstitial nephritis (BPG high doses)
- Cardiac Arrhythmia (lidocaine)
- Hypotension (lidocaine)
- Seizure (lidocaine)
- Bronchospasm, dyspnea (lidocaine)

Mild

• Hyperkalemia (BPG)

There is a risk of breach of confidentiality.

Benefits

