The potential benefit to the participant is that they would receive the treatment they normally would but with the potential benefit of less pain in the injection site with 1% lidocaine. As for the benefit to society, this may provide evidence that may change standard clinical practice with respect to how we perform benzathine penicillin G injections in the US and if lidocaine is shown to cause less pain, then it would become standard practice to include 1% lidocaine in each syringe of benzathine penicillin G.

2.f Early Withdrawal of Subjects, Including When and How to Withdraw Subjects

Early withdrawal of subjects will be handled by the principal investigator, with participants having the direct contact of the PI via email or phone, and through stating that they no longer would like to participate in the study. The PI also will have the right

to withdraw someone if upon evaluation of the patient, they meet certain exclusion criteria. All withdrawals will be done immediately and seeing as this study has short term

of participation, withdrawal should not be difficult.

2.g Data Collection and Follow-up for Withdrawn Subjects

Individuals who withdraw from the study will be noted as lost to follow up and no further data will be obtained from them. They will continue to receive standard of care within the outpatient clinical setting.

E3 Study Drug

3.a Description

1% lidocaine solution added to prefilled 1.2 million units Benzathine penicillin G.

3.b Treatment Regimen

0.5ml 1% lidocaine solution added to prefilled 1.2 million units Benzathine Pencillin G syringe

3.c Method for Assigning Subjects to Treatment Groups

Each participant will receive 2x 1.2 million units injection, one with lidocaine and one with normal saline, therefore each participant will serve as both treatment and control group.

3.d Preparation and Administration of Study Drug

Each syringe of BPG is prefilled. A nurse/MA will then add 0.5 ml 1% lidocaine solution to one BPG syringe, and 0.5ml normal saline solution to another BPG syringe. They will randomly syringes to be injected into the left gluteal muscle vs the right gluteal muscle via random assignment program. They will log the assignment with the unique patient code into a log book.

3.e Subject Compliance Monitoring

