Each log book entry will be entered into RedCap survey using the unique patient code and then the patient will fill out pain scale in RedCap using their unique code 10 minutes and 24 hours after injection through follow up email. If they do not respond to the 24 hour follow up email, a second email will be sent 48 hours after injection.

3.f Prior and Concomitant Therapy

Participants will be asked in the follow up survey about any other pain medications they have taken within the last 24 hours. They will also be asked about if this is their first treatment with respect to syphilis treatment, or if this is the second or third dose in a series of treatment. No other concomitant therapies would preclude individuals from participating in the study.

3.g Packaging

Both BPG syringes will look identical other than having one say L and one say R, based off randomization.

3.h Blinding of Study Drug

Both participants and clinicians will be blinded to the contents of the syringe. The nurse filling the syringe will assign the syringes randomly to be injected into L or R gluteal muscle and will label them accordingly, logging the designation in a log book that will remain blinded until the analysis portion of the study. The participant will be blinded as they will receive one site of injection with lidocaine and the other with normal saline, serving as their own intervention and control group.

3.i Receiving, Storage, Disposing and Return

BPG will be stored in the refrigerator in the Washington University St. Louis Infectious Diseases clinic, along with the lidocaine and normal saline solutions being kept in storage in the same clinic. All syringes will be disposed of in sharps containers, as well as used lidocaine ampules and normal saline syringes.

F Study Procedures

F1 Screening for Eligibility and Visit 1 (completed at one visit)

- 1- Participants with confirmed syphilis (RPR and treponemal test positive) who are receiving their first treatment injection of bicillin will be screened for participation in the study by infectious diseases clinicians, nurses, or Mas who interact with the patient during their injection visit. If patient is willing to participate, trial team will be notified. (15-30 minutes)
- 2- Trial team will assess patient for inclusion/exclusion criteria and ask if would like to be part of clinical trial. (5 minutes)

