- 3- The participant will then be taken to a clinic room and be shown the consent form. Study design will be explained to them including them receiving the same treatment they would normally but with one injection with 0.5 ml normal saline and one with 0.5 ml 1% lidocaine. They will then be asked if they have any questions and if they choose to consent, they will sign a physical consent form that will then be uploaded into their chart. (30-45 minutes)
- 4- Trial staff will then obtain the two injections and administer them one in each gluteal muscle. The patient will then be left for 15 minutes, after which they will fill out a pain score 0-10 for each injection site at 10 minutes post injection. (15-30 minutes)
- 5- Patient will then be informed they will receive an email survey (via RedCap) 24 hours

from trial staff to answer the same pain scale questions at that time. Exit counseling will occur and patient is then free to go. (15 minutes)

F2 Visit 2

Participants will receive an email from trial staff 24 hours after injection site to rate their pain from 0-10 at that time via online survey (RedCap) and to ask if any other pain medication was used in the last 24 hours and if they had any other symptoms/side effects. (5 minutes)

F3 Safety and Adverse Events

3.a Safety Monitoring

Patients will be asked about other side effects/adverse events during the 24 hour follow up. Patients can also contact providers through MyChart and/or through contacting the clinic/trial team.

3.b Medical Monitoring

i Investigator only

The investigator team will be monitoring the survey results for any signs of adverse effects. The monitoring will be ongoing and there will be an internal review of combined data every 6 months.

3.c Definitions of Adverse Events

Any undesirable experience associated with the use of medical product in patient. Common adverse events are listed above.

3.d Classification of Events

i Relationship

10 minutes after injection vs. 24 hours after injection

ii Severity

Mild, Moderate, or life threatening

iii Expectedness

Rare, other than injection site pain which is common

3.e Data Collection Procedures for Adverse Events

Adverse events will be asked about in the survey given 24 hours post injection.

3.f Reporting Procedures

Participants will report adverse events via a RedCap survey emailed 24 hours post injection. Other adverse events can be reported to PI or to clinic staff.

3.g Adverse Event Reporting Period

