Adverse events can be reported within 7 days post injection with participants having the ability to call for up to 7 days.

3.h Post-study Adverse Event

Any adverse event post study or the time listed above should be reported to the PI.

F4 Study Outcome Measurements and Ascertainment

The primary outcome measure will be pain rating scores from 0 (least pain) to 10 (most pain) at 10 minutes after injection in each injection site, as well as 24 hours after injection.

Secondary outcome measures will include adverse effects of lidocaine or benzathine penicillin G., such as allergic reactions or injection site reactions.

F5 Rationale for the Selection of Outcome Measures

Injection site pain is the most common adverse effect of Benzathine Penicillin G (BPG) intramuscular injections. For this reason, rating pain scales from 0-1 10 minutes and 24 hours after injection will allow us to measure immediate and longer term pain after injection, with and without lidocaine added to prefilled BPG syringes.

G Statistical Plan

G1 Sample Size Determination and Power

A sample size of 46 patients (92 injections) will be required to detect a clinically significant reduction in pain and discomfort associated with the injection of Bicillin, with a power of 80% and a significance level of 0.05.

G2 Interim Monitoring and Early Stopping

As this is a short term study with small population, it is not expected to stop early. Interim monitoring for adverse effects will occur at 6 months or after 24 participants have participated, whichever occurs first.

G3 Analysis Plan

Pain scores will be collected by trained study personnel. Data will be entered into a secure database and analyzed using statistical software. Descriptive statistics will be used to summarize the data, and t-tests or chi-squared tests will be used to compare pain scores and adverse effects between the treatment and control groups. They will also see if there any use of pain medications through descriptive statistics. Demographic data will also be collected.

G4 Statistical Methods

Descriptive statistics will be used to summarize the data, and t-tests or chi-squared tests will be used to compare pain scores and adverse effects between the treatment and control groups.

G5 Missing Outcome Data

Missing outcome data on follow up will be noted and statistical analysis will be performed on intention to treat model.

G6 Unblinding Procedures

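### The planned treatment-versus-control test of adverse effects has no comparator for systemic events, because every participant receives both syringes at one visit, and for non-pain site reactions it ignores pairing

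*Protocol*

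**What the plan says.** Protocol C2 sets the secondary aim: "To see if there are any adverse effects of adding 0.5 ml 1% lidocaine to prepackaged Benzathine Penicillin G". F4 names adverse effects of lidocaine or of benzathine penicillin G as secondary outcomes, "such as allergic reactions or injection site reactions". For the analysis, G3 and G4 both state that "t-tests or chi-squared tests will be used to compare pain scores and adverse effects between the treatment and control groups". Neither section separates events at an injection site from events of the whole person. G3 also plans descriptive statistics.

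The design is within-person. E3 3.c gives each participant one syringe of each kind, "therefore each participant will serve as both treatment and control group", and E3 3.h repeats that the participant is "serving as their own intervention and control group". F1 places both injections in a single visit.

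At 24 hours, F2 describes the adverse-event item as a question on other pain medication "and if they had any other symptoms/side effects". E2 2.d says of the record of which side had lidocaine: "This log book will then be used to cross reference injection sites and the survey results during the analysis phase".

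**The concern.** A test between treatment and control needs some persons, sites or periods with lidocaine and some without. For pain, each injection site is scored, so that contrast exists. For dizziness, arrhythmia or anaphylaxis it does not: all participants have had lidocaine by the time they can report anything, and none has had saline alone.

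The risk lies in interpretation. A test with no comparator can still produce a p-value, and a non-significant one could be read as evidence that lidocaine adds no adverse effects. E2 2.e foresees lidocaine becoming standard practice if it is shown to reduce pain, so the safety statement beside the pain result will be relied on.

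A smaller, separate matter concerns non-pain site reactions. These can be compared, but the two sites of one person are not independent, and an ordinary chi-squared test treats them as if they were.

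**Working it through.** **1. Which events lack a comparator.** E2 2.e marks 14 risks as lidocaine risks:
- common: headache, transient pain, edema (3)
- less common: agitation, anxiety, confusion, dizziness, lethargy, tinnitus (6)
- life-threatening: anaphylaxis (1)
- rare serious: arrhythmia, hypotension, seizure, bronchospasm/dyspnea (4)

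3 + 6 + 1 + 4 = 14. Only transient pain and edema can be located at a syringe site, so 14 − 2 = 12 belong to the whole person.

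**2. What the stated test gives for them.** G1 plans 46 patients; assume that all are analysed. Exposed to lidocaine: 46. Not exposed: 0. If x participants have an event and it is counted under both syringes, the table is x/46 against x/46. For x = 5 this is 5/46 against 5/46, with chi-squared = 0 and p = 1, and the same holds for any x from 1 to 45. A paired test does not help, because there are no discordant pairs. If each event is assigned to one syringe instead, the result depends on an arbitrary rule.

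**3. What can be reported for them.** Exact (Clopper-Pearson) two-sided 95% intervals per participant:
- 0/46: upper limit 1 − 0.025^(1/46) = 7.7%
- 1/46: 0.06% to 11.5%
- 2/46: 0.5% to 14.8%

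The chance of seeing at least one event is 1 − (1 − p)^46, which is 37%, 61% and 91% at true risks of 1%, 2% and 5%.

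**4. Non-pain site reactions.** The protocol gives no rates. F3 3.d describes expectedness as "Rare, other than injection site pain which is common", while E2 2.e lists edema as common. The rates below are therefore assumptions over a range, as is the within-person correlation of 0.3. The figures come from full enumeration of the paired 2×2 table with n = 46, at two-sided 0.05 and without continuity correction.

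| True rates | Chi-squared | Mid-p McNemar | Exact McNemar |
|---|---|---|---|
| 5% both (type I error) | 0.020 | 0.009 | 0.002 |
| 10% both | 0.026 | 0.030 | 0.012 |
| 20% both | 0.021 | 0.042 | 0.023 |
| 30% both | 0.019 | 0.045 | 0.026 |
| 40% both | 0.018 | 0.047 | 0.028 |
| 40 vs 20% (power) | 57% | 70% | 61% |
| 20 vs 10% | 24% | 32% | 22% |
| 10 vs 5% | 12% | 11% | 5% |
| 10 vs 2% | 37% | 30% | 16% |

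The value near 0.02 follows from the variance. With correlation 0.3, the true variance of the difference under equal rates is 0.7 times the variance that an unpaired test assumes. The effective critical value is 1.96/√0.7 = 2.34, for which the two-sided error is 0.019.

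At zero correlation, 40 vs 20% gives power of 56%, 53% and 46%. Pairing therefore does not raise power in general.

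Exact McNemar needs at least 6 discordant pairs, all in one direction, to reach significance: 2 × 0.5^6 = 0.031, whereas 5 pairs give 0.0625.

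**The case against.** Much can be said for the plan.

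- **Aim C2 is not defeated.** A reader might infer that C2 cannot be addressed at all for systemic events. The text does not support that: C2 asks whether adverse effects occur and names neither a test nor a saline contrast, and G3 already plans descriptive statistics. What fails is the between-group test.
- **A valid comparison of adverse effects survives.** A reader might infer that none remains if the survey does not record side. That is wrong too. F5 calls injection site pain the most common adverse effect of the penicillin injection, and pain is scored for each site at 10 minutes and asked about again with the same questions at 24 hours. Any gap concerns non-pain reactions only.
- **Double counting is not stated.** Nothing says that a systemic event will be entered under both syringes. That is one possible coding. The point does not depend on it, since no other coding supplies a comparator.
- **The survey form is not shown.** It may hold left/right items, so their absence cannot be asserted. The log book records which side had lidocaine, but it cannot supply the side of a symptom reported without one. Calls and reports within the 7-day period might recover some of this.
- **The analysis plan could sort this out.** It could separate local from systemic events, and F4 does not say that the allergic reactions it names are only systemic. But the protocol itself fixes a test of adverse effects without that limit, and no analysis plan can create a lidocaine-free comparator.
- **Chi-squared is conservative here.** Its type I error stays below 0.05 at the assumed correlation, and it has more power than McNemar in some settings. This is so; the reason to change is that the test assumes independence that the design rules out.

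**Conclusion.** The point holds in a limited form. As written, G3 and G4 plan a lidocaine-versus-saline test that is not valid for systemic events, which are 12 of the 14 listed lidocaine risks and include systemic allergic reactions. This follows from the design alone and rests on no assumed rate. The test named for non-pain site reactions ignores pairing. Its type I error is about 0.02 at assumed rates of 20-40% and correlation 0.3, and it would differ at other correlations. The defect does not reach the pain outcome, nor the descriptive part of C2. It merits correction because a p-value from a test without a comparator could be mistaken for evidence of safety.

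**What to change.** In G3 and G4:
1. Restrict the lidocaine-versus-saline comparison of adverse effects to reactions attributable to one injection side.
2. State that these are analysed as matched pairs, for example by McNemar's test (mid-p or exact), because the two sites of one person are not independent.
3. Report systemic events per participant, descriptively, with exact 95% confidence intervals, labelled as exposed to both syringes and with no lidocaine-versus-saline conclusion.

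Check that the 24-hour survey records non-pain site reactions separately for left and right, and add these items if it does not.

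The cost is a change of wording and possibly a few survey items. The downsides are a narrower safety comparison, possibly a slightly longer survey, and low power if site reactions are rare (5-11% for 10 vs 5% with exact or mid-p McNemar, under the assumptions above).

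### G3 and G4 plan an ordinary chi-squared test for adverse effects, but the injections are paired within participant, counts will often be sparse, and systemic events cannot be assigned to either syringe

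*Protocol*

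**What the plan says.** G3 and G4 of the protocol carry the same sentence: "t-tests or chi-squared tests will be used to compare pain scores and adverse effects between the treatment and control groups". For an event that is present or absent, this means a chi-squared test. Neither section names a paired test, an exact test or a rule for small counts. Both also promise descriptive statistics.

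Other sections bear on whether that test fits:

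- **Design.** E3 3.c gives every participant both injections, so each person is treated and control at once. E2 2.b says the same.
- **Size.** G1 states "A sample size of 46 patients (92 injections) will be required to detect a clinically significant reduction in pain", that is, 46 injections per treatment. The number is justified for pain only.
- **Aim.** C2 is "To see if there are any adverse effects of adding 0.5 ml 1% lidocaine to prepackaged Benzathine Penicillin G". F4 names allergic reactions and injection site reactions as examples.
- **Frequency.** F3 3.d iii classes events as "Rare, other than injection site pain which is common", and E2 2.e opens with "Risks are rare and mainly involve injection site pain, allergic reaction". The list in E2 2.e nevertheless places "Headache (lidocaine"), transient pain and edema under the likely or common heading. No numerical rate is given.
- **Collection.** F2 and F3 3.e describe a general question at 24 hours about other symptoms or side effects. No attribution to an injection site is described.

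**The concern.** The planned test does not match the data in three ways.

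1. **Pairing.** A chi-squared test on a 2×2 table of treatment by event assumes 92 independent observations. Here there are 46 people with two observations each. A person prone to local reactions may react on both sides, and only those who react on one side carry information about lidocaine.
2. **Sparse counts.** For events as rare as F3 3.d iii suggests, the large-sample approximation has little support at 46 per treatment. A single table can fall on either side of 0.05 depending on the version of the test.
3. **Attribution.** A headache or an allergic reaction belongs to the participant, who has received both syringes. There is no control group for such an event, so a treatment-versus-control table cannot be filled in.

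At stake is the secondary safety aim. E2 2.e expects lidocaine to become standard practice if it reduces pain, so the safety statement published with the pain result will be read closely.

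**Working it through.** **Inputs.** 46 participants and 46 injections per treatment (G1); both injections in each participant (E3 3.c). Event rates are not in the protocol, so those used below are assumptions shown as a range. The plan gives no figure for adverse effects to reproduce.

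**Step 1: expected counts.** The expected number of events per treatment is 46 × rate: 0.46 at 1%, 0.92 at 2%, 2.3 at 5% and 4.6 at 10%. The customary minimum of 5 needs a rate of 5/46 = 10.9%.

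**Step 2: single sparse tables.** For a v b events among 46 and 46, uncorrected Pearson is X² = 92(a(46−b) − b(46−a))² / [(a+b)(92−a−b)·46·46].

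- 4 v 0: X² = 92 × 184² / (4 × 88 × 2116) = 4.18, p = 0.041.
- 6 v 1: X² = 92 × (270 − 40)² / (7 × 85 × 2116) = 3.87, p = 0.049.

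The exact McNemar test uses only participants who react at one site. If nobody reacts at both sites:

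- 4 v 0: 2 × 0.5⁴ = 0.125.
- 6 v 1: 2 × (1 + 7)/2⁷ = 0.125.

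| Lidocaine v saline | Pearson, uncorrected | Pearson, continuity-corrected | Fisher | Exact McNemar |
|---|---|---|---|---|
| 4 v 0 | 0.041 | 0.125 | 0.117 | 0.125 |
| 5 v 0 | 0.021 | 0.066 | 0.056 | 0.063 |
| 6 v 0 | 0.011 | 0.035 | 0.026 | 0.031 |
| 6 v 1 | 0.049 | 0.116 | 0.111 | 0.125 |

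The large-sample McNemar test does not cure sparsity: for 4 v 0 it gives (4 − 0)²/4 = 4, p = 0.046.

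**Step 3: long-run type I error of uncorrected Pearson.** Exact enumeration, treating the two injections as independent, gives 0.15% at a 1% rate, 1.1% at 2%, 5.0% at 5%, 6.1% at 8%, 5.9% at 10% and 5.1% at 20%. Among the rates examined the peak is about 6%. For truly rare events the test is conservative.

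**Step 4: effect of ignoring the pairing.** With a within-person correlation of 0.3 (assumed), simulation puts the type I error of the same test at 2.0% at a 5% rate and 2.1% at a 20% rate. With correlation 0.6 it is 0.3% at both. An unpaired test on positively correlated pairs is therefore too cautious and can miss a real difference.

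An invented example shows this. Let 10 participants react at both sites, 8 at the lidocaine site only and 1 at the saline site only. The unpaired table is 18 v 11, so X² = 92 × (18×35 − 11×28)² / (29 × 63 × 2116) = 2.47, p = 0.116. Exact McNemar on 8 v 1 gives 2 × (1 + 9)/2⁹ = 0.039.

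**Step 5: what zero events would show.** The Clopper-Pearson two-sided 95% upper limit for 0 of 46 is 1 − 0.025^(1/46) = 7.7%. The chance of seeing no event is (1 − rate)⁴⁶: 63% at a true rate of 1%, 39% at 2% and 9% at 5%.

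**Step 6: attribution.** F2 sets one general question per participant. For a systemic event the answer has no treatment label, so neither a chi-squared nor an exact between-treatment test can be formed.

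**The case against.** Several objections carry weight.

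- **The protocol does not say which chi-squared test.** With the continuity correction, 4 v 0 gives 0.125, the same as exact McNemar. This stands. A reader might infer that the planned test will over-call harm in general; Step 3 does not support that. The fault lies in individual sparse tables and in the choice being left open, and the correction does nothing about pairing.
- **Not every adverse effect is rare.** This also stands. F3 3.d iii exempts injection site pain, and E2 2.e lists headache, transient pain and edema as common. Above about 11% the small-count argument lapses. The pairing argument then matters more, and the attribution argument is unaffected.
- **The protocol never claims safety from a non-significant test.** A reader might infer that few events would be reported as no adverse effects. No section says so: C2 asks only whether there are any. The 7.7% limit is useful context for reporting and does not correct a stated conclusion.
- **Descriptive reporting is already planned, and detail may sit in an analysis plan not shown.** Counts would indeed be reported. But the two sections go further and name a test, and an analysis plan that followed them would inherit a method that does not fit the design.

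**Conclusion.** The point holds as a minor one. The test named in G3 and G4 assumes independent groups in a design where each participant is their own control. It rests on a large-sample approximation that is unsupported for events under about 11%, and it cannot be applied to systemic events at all. In sparse tables the uncorrected p-value can be about a third of the exact paired one (0.041 v 0.125 at 4 v 0). Long-run type I error, by contrast, stays at or below about 6% at the rates examined, and falls lower still when the two sites are positively correlated.

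These conclusions assume 46 participants with complete data. The exact McNemar values in the table assume that no one reacts at both sites, and the event rates and correlations are assumed. The attribution point rests on adverse events being collected as F2 and F3 3.e describe; local reactions could still be recorded by site if the survey form allows it. No decision rule depends on the adverse-effect p-value, and the pain outcome is untouched by this point.

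**What to change.** In G3 and G4, remove chi-squared tests for adverse effects and state instead:

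- **Local reactions recorded by injection site:** report how many participants reacted at both sites, at the lidocaine site only, at the saline site only and at neither, with an exact McNemar (binomial) p-value on the two one-site counts.
- **Systemic events:** report the number of participants with each event and its exact (Clopper-Pearson) 95% interval, with no between-treatment test. Note that 0 of 46 still allows a rate up to about 7.7%.

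Fisher's exact test would deal with the small counts but not with the pairing, so it is not a substitute.

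The cost is two sentences and no extra participants. If the 24-hour survey does not already ask about local reactions separately for left and right, it needs to. There are two downsides. The safety statement becomes less favourable, and the exact test has little power when events are few: it cannot reach p < 0.05 with fewer than 6 participants reacting at one site only, even if all are on the lidocaine side.
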